6.2 Dose modifications for ibrutinib

Interrupt ibrutinib for any Grade 3 or greater non-hematological, Grade 3 or greater neutropenia with infection or fever, or Grade 4 hematological toxicities. Once the symptoms of the toxicity have resolved to Grade 1 or baseline, reinitiate ibrutinib at the starting dose. If the toxicity reoccurs, reduce dose by one capsule (140 mg per day).

NOTE: As diarrhea could occur from the use of ibrutinib or nivolumab, patients with grade 2 diarrhea should have their ibrutinib held.

Recommended dose modifications are described below:

Toxicity Occurrence	Dose modification Starting Dose = 420 mg daily
First	Restart at 420 mg daily
Second	Restart at 280 mg daily
Third	Restart at 140 mg daily
Fourth	Discontinue ibrutinib

Dose Modifications for Use with CYP3A Inhibitors/Inducers: Ibrutinib is metabolized primarily by CYP3A. Concomitant use of strong CYP3A inhibitors which would be taken chronically (e.g., ritonavir, indinavir, nelfinavir, saquinavir, boceprevir, telaprevir, nefazodone) is not recommended. For strong CYP3A inhibitors used short-term (e.g., antifungals and antibiotics for 7 days or less, e.g., ketoconazole, itraconazole, voriconazole, posaconazole, clarithromycin, telithromycin), consider holding ibrutinib therapy during the duration of the inhibitor use. Avoid strong CYP3A inhibitors that are needed chronically. If a moderate CYP3A inhibitor must be used (e.g., fluconazole, darunavir, erythromycin, diltiazem, atazanavir, aprepitant, amprenavir, fosamprevir, verapamil, grapefruit products and ciprofloxacin), reduce ibrutinib dose to 140 mg daily.

Avoid grapefruit and Seville oranges during ibrutinib treatment, as these contain moderate inhibitors of CYP3A. Avoid Star fruit as it contains inhibitors of CYP3A.

Administration of ibrutinib with strong inducers of CYP3A can decrease ibrutinib plasma concentrations. Concomitant use of strong CYP3A inducers (e.g., rifampin, rifabutin, phenytoin, carbamazepine, and St. John's Wort) are not recommended.

A list of common CYP3A inhibitors and inducers is provided in Appendix 2; a comprehensive list of inhibitors, inducers, and substrates may be found at

<http://medicine.iupui.edu/clinpharm/ddis/table.aspx>. This website is continually revised and should be checked frequently for updates.

7.0 CONCOMITANT THERAPY

7.1 Allowed concomitant therapy

Patients should receive full supportive care during study participation, including hematopoietic growth factors, transfusion of blood products, fluid and electrolyte replacement, and antibiotics when appropriate.

7.2 Excluded concomitant therapy

Use of the following therapies is prohibited during the study:

- Cytotoxic chemotherapy
- Immunotherapy (outside of this study)
- Radiotherapy (Note: Localized radiotherapy to an area not compromising bone marrow function is allowed)
- Any therapies intended for the treatment of lymphoma/leukemia whether FDA-approved or experimental (outside of this study)
- Steroid therapy for anti-neoplastic intent. Inhaled steroids for asthma, topical steroids, steroids as part of premedication for nivolumab, or replacement/stress corticosteroids are permitted.
- Strong CYP3A inhibitors which would be taken chronically
- Grapefruit, Seville oranges, Star fruit
- Strong CYP3A inducers (e.g., rifampin, rifabutin, phenytoin, carbamazepine, and St. John's Wort) are not recommended

8.0 PRETREATMENT EVALUATIONS

1. Pretreatment evaluation will include a complete history and physical examination including vital signs, neurological examination, ECOG performance status, height and weight and recording of concurrent medications (within 14 days of the first dose)
2. Complete blood count (hemoglobin, white blood cell count, platelet count, white blood count differential) (within 14 days of the first dose)
3. Clinical laboratory evaluation will include serum sodium, potassium, calcium, BUN, creatinine, glucose, phosphorous, magnesium, albumin, total protein, alkaline phosphatase, total bilirubin, ALT, AST, uric acid, LDH, amylase, lipase, β -2 microglobulin, immunoglobulins (within 14 days of the first dose)
4. B, T, NK cell counts and subset analyses on the peripheral blood (within 14 days of the first dose)
5. PT, aPTT (within 14 days of the first dose)
6. Urinalysis (within 14 days of the first dose)
7. HIV Ab, Hepatitis C ab, HBsAg, anti-HBcAb (within 30 days of the first dose)
8. TSH, Free T4 (within 30 days of the first dose)
9. Women of childbearing potential must have a negative serum or urine β -hCG pregnancy test result within 24 hours prior to the first dose.
10. 12-lead EKG (within 30 days of the first dose)
11. MUGA or Echocardiogram (within 30 days of the first dose)
12. Bone marrow aspiration and biopsy (within 60 days of the first dose if no intervening treatment for CLL given)
13. CT scan of the neck (if indicated), chest, abdomen, and pelvis with IV and oral contrast, within 30 days of the first dose with no intervening treatment for CLL given. Patients with palpable cervical lymphadenopathy noted at screening physical examinations should have imaging of the neck included in their screening imaging studies and at subsequent time points for response assessment.
Note: PET scan may be used instead of the CT scan imaging.

9.0 EVALUATIONS DURING THE STUDY

Cycle 1 Day 1

1. CBC, platelet count and differential; serum sodium, potassium, calcium, BUN, creatinine, glucose, phosphorous, magnesium, albumin, total protein, alkaline phosphatase, total bilirubin, ALT, AST, uric acid, LDH (Note: Cycle 1 Day 1 labs obtained within 3 days prior to the Day 1 is acceptable)
2. Vital signs, history and physical examination including neurological examination (Note: History and physical examination within 3 days prior to the Day 1 is acceptable)

Cycle 1 Day 8 (+/- 3 days)

1. CBC, platelet count and differential; serum sodium, potassium, calcium, BUN, creatinine, glucose, phosphorous, magnesium, albumin, total protein, alkaline phosphatase, total bilirubin, ALT, AST, uric acid, LDH
2. Vital signs, history and physical examination including neurological examination

Cycle 1 Day 15 (+/- 3 days)

1. CBC, platelet count and differential; serum sodium, potassium, calcium, BUN, creatinine, glucose, phosphorous, magnesium, albumin, total protein, alkaline phosphatase, total bilirubin, ALT, AST, uric acid, LDH, amylase, lipase
2. Vital signs, history and physical examination including neurological examination
3. Urinalysis

Cycle 1 Day 22 (+/- 3 days)

1. CBC, platelet count and differential; serum sodium, potassium, calcium, BUN, creatinine, glucose, phosphorous, magnesium, albumin, total protein, alkaline phosphatase, total bilirubin, ALT, AST, uric acid, LDH
2. Vital signs, history and physical examination including neurological examination

End of Cycle 1 (+/- 3 days)

1. For COHORT 1 only - CT scan of the neck (if indicated), chest, abdomen, and pelvis with IV and oral contrast. PET scan may be used instead of the CT scan imaging. Note: This evaluation should be done prior to starting ibrutinib in this cohort (i.e. prior to starting cycle 2).
2. For COHORT 1 only – Bone marrow aspiration with multi-color flow cytometry for MRD evaluation.

Cycle 2 Day 1 (+/- 3 days)

1. CBC, platelet count and differential; serum sodium, potassium, calcium, BUN, creatinine, glucose, phosphorous, magnesium, albumin, total protein, alkaline phosphatase, total bilirubin, ALT, AST, uric acid, LDH, amylase, lipase, quantitative immunoglobulin levels, and B, T, NK cell counts and subset analyses on the peripheral blood
2. Vital signs, history and physical examination including neurological examination
3. TSH, Free T4
4. Urinalysis

Cycle 2 Day 8 (+/- 3 days)

1. CBC, platelet count and differential; serum sodium, potassium, calcium, BUN, creatinine, glucose, phosphorous, magnesium, albumin, total protein, alkaline phosphatase, total bilirubin, ALT, AST, uric acid, LDH

Cycle 2 Day 15 (+/- 3 days)

1. CBC, platelet count and differential; serum sodium, potassium, calcium, BUN, creatinine, glucose, phosphorous, magnesium, albumin, total protein, alkaline phosphatase, total bilirubin, ALT, AST, uric acid, LDH, amylase, lipase
2. Serum or urine β -hCG pregnancy test (for women of childbearing potential)
3. Vital signs, history and physical examination including neurological examination

Cycle 2 Day 22 (+/- 3 days)

1. CBC, platelet count and differential; serum sodium, potassium, calcium, BUN, creatinine, glucose, phosphorous, magnesium, albumin, total protein, alkaline phosphatase, total bilirubin, ALT, AST, uric acid, LDH

Cycle 3 Day 1 (+/- 3 days)

1. CBC, platelet count and differential; serum sodium, potassium, calcium, BUN, creatinine, glucose, phosphorous, magnesium, albumin, total protein, alkaline phosphatase, total bilirubin, ALT, AST, uric acid, LDH, amylase, lipase, quantitative immunoglobulin levels and B, T, NK cell counts and subset analyses on the peripheral blood
2. Vital signs, history and physical examination including neurological examination
3. TSH, Free T4
4. Urinalysis

Cycle 3 Day 8 (+/- 3 days)

1. CBC, platelet count and differential; serum sodium, potassium, calcium, BUN, creatinine, glucose, phosphorous, magnesium, albumin, total protein, alkaline phosphatase, total bilirubin, ALT, AST, uric acid, LDH

Cycle 3 Day 15 (+/- 3 days)

1. CBC, platelet count and differential; serum sodium, potassium, calcium, BUN, creatinine, glucose, phosphorous, magnesium, albumin, total protein, alkaline phosphatase, total bilirubin, ALT, AST, uric acid, LDH, amylase, lipase
2. Vital signs, history and physical examination including neurological examination

Cycle 3 Day 22 (+/- 3 days)

1. CBC, platelet count and differential; serum sodium, potassium, calcium, BUN, creatinine, glucose, phosphorous, magnesium, albumin, total protein, alkaline phosphatase, total bilirubin, ALT, AST, uric acid, LDH

End of Cycle 3 (+/- 1 week)

1. Bone marrow aspiration and biopsy with multi-color flow cytometry for MRD evaluation.
2. CT scan of the neck (if indicated), chest, abdomen, and pelvis with IV and oral contrast. PET scan may be used instead of the CT scan imaging.

Cycle 4 Day 1 (+/- 3 days)

1. CBC, platelet count and differential; serum sodium, potassium, calcium, BUN, creatinine, glucose, phosphorous, magnesium, albumin, total protein, alkaline phosphatase, total bilirubin, ALT, AST, uric acid, LDH, amylase, lipase, β -2 microglobulin, quantitative immunoglobulin levels and B, T, NK cell counts and subset analyses on the peripheral blood
2. Vital signs, history and physical examination including neurological examination
3. TSH, Free T4
4. Urinalysis
5. Serum or urine β -hCG pregnancy test (for women of childbearing potential)

Cycle 4 Day 15 (+/- 3 days)

1. CBC, platelet count and differential; serum sodium, potassium, calcium, BUN, creatinine, glucose, phosphorous, magnesium, albumin, total protein, alkaline phosphatase, total bilirubin, ALT, AST, uric acid, LDH, amylase, lipase

2. Vital signs, history and physical examination including neurological examination

Cycle 5 Day 1 (+/- 3 days)

1. CBC, platelet count and differential; serum sodium, potassium, calcium, BUN, creatinine, glucose, phosphorous, magnesium, albumin, total protein, alkaline phosphatase, total bilirubin, ALT, AST, uric acid, LDH, amylase, lipase, quantitative immunoglobulin levels and B, T, NK cell counts and subset analyses on the peripheral blood
2. Vital signs, history and physical examination including neurological examination

Cycle 5 Day 15 (+/- 3 days)

1. CBC, platelet count and differential; serum sodium, potassium, calcium, BUN, creatinine, glucose, phosphorous, magnesium, albumin, total protein, alkaline phosphatase, total bilirubin, ALT, AST, uric acid, LDH, amylase, lipase
2. Serum or urine β -hCG pregnancy test (for women of childbearing potential)
3. Vital signs, history and physical examination including neurological examination

Cycle 6 Day 1 (+/- 3 days)

1. CBC, platelet count and differential; serum sodium, potassium, calcium, BUN, creatinine, glucose, phosphorous, magnesium, albumin, total protein, alkaline phosphatase, total bilirubin, ALT, AST, uric acid, LDH, amylase, lipase, quantitative immunoglobulin levels and B, T, NK cell counts and subset analyses on the peripheral blood
2. Vital signs, history and physical examination including neurological examination

Cycle 6 Day 15 (+/- 3 days)

1. CBC, platelet count and differential; serum sodium, potassium, calcium, BUN, creatinine, glucose, phosphorous, magnesium, albumin, total protein, alkaline phosphatase, total bilirubin, ALT, AST, uric acid, LDH, amylase, lipase
2. Vital signs, history and physical examination including neurological examination

End of Cycle 6 (+/- 1 week)

1. Bone marrow aspiration and biopsy with multi-color flow cytometry for MRD evaluation.
2. CT scan of the neck (if indicated), chest, abdomen, and pelvis with IV and oral contrast. PET scan may be used instead of the CT scan imaging.

Cycle 7 onwards (+/- 3 days)

1. CBC, platelet count and differential; serum sodium, potassium, calcium, BUN, creatinine, glucose, phosphorous, magnesium, albumin, total protein, alkaline phosphatase, total bilirubin, ALT, AST, uric acid, LDH, amylase, lipase (on the day of Nivolumab infusions)
2. Complete history and physical examination including vital signs and neurological examination at least monthly.
3. Quantitative immunoglobulin levels every month
4. B, T, NK cell counts and subset analyses on the peripheral blood every 3 months
5. Serum or urine β -hCG pregnancy test (for women of childbearing potential) at least every 6 weeks
6. TSH, Free T4 every 3 months

7. Urinalysis every 3 months
8. Bone marrow aspiration and biopsy with multi-color flow cytometry for MRD evaluation every 3 months for the first year of the study, then every 6 months
9. CT scan of the neck (if indicated), chest, abdomen, and pelvis with IV and oral contrast every 3 months for the first year of the study, then every 6 months. PET scan may be used instead of the CT scan imaging.

Note: Patients who complete all protocol specified nivolumab treatments (or discontinue nivolumab early, see Section 12.0) will have the following evaluations until removal from study (These are the patients continuing on ibrutinib monotherapy):

1. CBC, platelet count and differential; serum sodium, potassium, calcium, BUN, creatinine, glucose, phosphorous, magnesium, albumin, total protein, alkaline phosphatase, total bilirubin, ALT, AST, uric acid, LDH at least monthly for the first 3 months, then every 3 months
2. Complete history and physical examination including vital signs and neurological examination at least monthly for the first 3 months, then every 3 months.
3. Quantitative immunoglobulin levels monthly for the first 3 months, then every 3 months
4. B, T, NK cell counts and subset analyses on the peripheral blood monthly for the first 3 months, then every 3 months
5. Serum or urine β -hCG pregnancy test (for women of childbearing potential) monthly for 3 times
6. TSH, Free T4 every 3 months
7. Urinalysis every 3 months
8. Bone marrow aspiration and biopsy with multi-color flow cytometry for MRD evaluation every 3 months for the first year of the study, then every 6 months
9. CT scan of the neck (if indicated), chest, abdomen, and pelvis with IV and oral contrast every 3 months for the first year of the study, then every 6 months. PET scan may be used instead of the CT scan imaging.

End of Study Visit – Patients, who are taken off study for any reason, will have an end of study visit. The end of study visit will occur 30 days +/- 7 days after the last dose of the study drugs. At this visit, the patient will have labs (CBC, platelet count and differential, sodium, potassium, calcium, BUN, creatinine, glucose, phosphorous, magnesium, albumin, total protein, alkaline phosphatase, total bilirubin, ALT, AST, uric acid, LDH), history and physical examination including neurological examination, serum immunoglobulins, B, T, NK cell counts and subset analyses on the peripheral blood, bone marrow aspiration and biopsy with multi-color flow cytometry for MRD evaluation (if the previous bone marrow evaluation was >3 months ago), and CT or PET imaging (if the previous CT or PET imaging was >3 months ago).

After completion of all protocol related treatments, patients will be followed for at least one year with at least monthly labs (CBC, platelet count and differential, sodium, potassium, calcium, BUN, creatinine, glucose, phosphorous, magnesium, albumin, total protein, alkaline phosphatase, total bilirubin, ALT, AST, uric acid, LDH), at least monthly history and physical examination, serum immunoglobulins every 3 months, B, T, NK cell counts and subset analyses on the peripheral blood every 3 months, bone marrow aspiration and biopsy with multi-color flow cytometry for MRD evaluation every 3-6 months, and CT or PET imaging every 3-6 months. Note: This post-protocol follow-up period of one year will end early if the

patient starts another treatment for their CLL/SLL. Inability to comply with these post-protocol follow-up evaluations will not be considered a protocol-deviation.

Adverse Events Monitoring - Adverse events will be assessed continually while on the study, until 30 days after the last dose of drug

NOTE: All treatments with nivolumab must be administered at the MDACC. During the first cycle all laboratory evaluations will be done at MDACC. Subsequently, the patient may have laboratory work and physical examination done at a local clinic and the results reported to the research nurse for the study. The laboratory work done at a local clinic will be forwarded to the patient's attending physician at MDACC, or PI of the study, who will sign off on the labs to verify that the results have been reviewed.

Outside Physician Participation During Treatment

1. MDACC Physician communication with the outside physician is required prior to the patient returning to the local physician. This will be documented in the patient record
2. A letter to the local physician outlining the patient's participation in a clinical trial will request local physician agreement to supervise the patient's care (Appendix 3)
3. Protocol required evaluations outside MDACC will be documented by fax. Faxed evaluations will be dated and signed by the MDACC physician/investigator indicating that they have reviewed it.
4. A copy of the informed consent, protocol abstract, treatment schema and evaluation during treatment will be provided to the local physician.
5. Documentation to be provided by the local physician will include progress notes, reports of protocol required laboratory and diagnostic studies and documentation of any hospitalizations.
6. The home physician will be requested to report to the MDACC physician/investigator all life threatening events within 24 hours of documented occurrence.

10.0 CRITERIA FOR RESPONSE

Response will be assessed by the investigator, based on physical examinations, CT scans, laboratory results, and bone marrow examinations, according to the modified 2008 IWCLL response criteria for CLL. OR is defined as a CR or PR (or CR with incomplete marrow recovery) as determined by investigator assessment using CLL response criteria.^{53,54} Patients with missing or no response assessments will be classified as non-responders.

Complete Response (CR): Requires all of the following:

- Peripheral blood lymphocytes <4000/ μ L
- Absence of significant lymphadenopathy (eg, lymph nodes >1.5 cm in diameter) by physical exam and CT (PET may be used in place of CT scan)

- No hepatomegaly or splenomegaly by physical exam (and CT/PET scan if assessment was abnormal before therapy or if physical exam is inconclusive)
- Absence of constitutional symptoms
- Blood counts above the following values (without need for growth factors or transfusions): neutrophils $>1,500/\mu\text{L}$, platelets $>100,000/\mu\text{L}$, hemoglobin $>11.0 \text{ g/dL}$
- Bone marrow aspirate and biopsy must be normocellular for age with $<30\%$ of nucleated cells being lymphocytes. Lymphoid nodules should be absent. If the bone marrow is hypocellular, a repeat determination should be made in 4 weeks or when peripheral blood counts have recovered. Hypocellular marrow should be noted as **CR with incomplete marrow recovery (CRI)**.

Partial Response (PR): Requires one of the following for a period ≥ 2 months:

- $\geq 50\%$ decrease in peripheral lymphocyte count from pretreatment baseline value
- $\geq 50\%$ reduction in lymphadenopathy as defined by:
 - $\geq 50\%$ decrease in lymph node size either in the sum products of up to 6 lymph nodes or in the largest diameter of the enlarged lymph node(s) detected before therapy
 - No increase in any lymph node and no new enlarged lymph node (In small lymph nodes [$<2\text{cm}$], an increase of $<25\%$ is not considered significant)
- $\geq 50\%$ reduction in pretreatment enlargement of the spleen or liver, as detected by CT/PET scan

Additionally, these patients must have at least one of the following for ≥ 2 months:

- Neutrophils $>1,500/\mu\text{L}$ (without need for growth factors)
- Platelets $>100,000/\mu\text{L}$ or $\geq 50\%$ improvement over baseline (without need for growth factors)
- Hemoglobin $>11.0 \text{ g/dL}$ (untransfused) or $\geq 50\%$ improvement over baseline

Additionally, patients who fulfill the criteria above for CR but who have the following will be considered a PR

- Patients with bone marrow nodules (may be noted as **nodular PR**). Immunohistochemistry should be performed to define whether these nodules are composed of primarily T cells or lymphocytes other than CLL cells, or CLL cells.
- Patients with persistent anemia or thrombocytopenia or neutropenia apparently unrelated to disease activity and more likely the consequence of persistent drug toxicity (may be noted as **CRI**).

Progressive Disease (PD): Characterized by ≥ 1 of the following events:

- Lymphadenopathy: $\geq 50\%$ increase in greatest determined diameter of any previous site; appearance of any new lesion, such as enlarged lymph nodes ($>1.5 \text{ cm}$), splenomegaly, hepatomegaly, or other organ infiltrates (NOTE: new lesion or isolated and/or transient increase in target lesion(s) in the setting of reduced lymph node size or organomegaly, or improvement in hemoglobin/platelets is not considered PD unless persists for >4 weeks (CT/PET scan confirmation required)
- $\geq 50\%$ increase in the previously noted enlargement of the liver or spleen; de novo appearance of hepatomegaly or splenomegaly

- $\geq 50\%$ increase in the absolute number of circulating lymphocytes to $\geq 5,000/\mu\text{L}$ (NOTE: In the absence of other objective evidence of PD, lymphocytosis alone is not considered progressive disease)
- Transformation to a more aggressive histology (i.e., Richter's syndrome)
- Occurrence of cytopenia (neutropenia, anemia, or thrombocytopenia) attributable to CLL (decrease in hemoglobin ≥ 2 gm/dL or to <100 g/L; or decrease $\geq 50\%$ in platelets or to $<100,000/\mu\text{L}$) that occurs ≥ 3 months after treatment, if the marrow biopsy demonstrates an infiltrate of clonal CLL cells.

Stable Disease (SD): Patients who do not fulfill the criteria for complete or partial response as defined above but do not exhibit progressive disease will be considered as having stable disease.

Responses for patients with RT will be assessed by non-Hodgkin's lymphoma (NHL) criteria.⁵⁵

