1.0 OBJECTIVES

Primary Objectives

1. To determine the efficacy (response rate) of nivolumab in combination with ibrutinib in patients with relapsed/refractory or high-risk untreated CLL by
 - a. Cohort 1: determine the response rate (CR/CRi) by 2008 IWCLL criteria
 - b. Cohort 2: determine the conversion rate from PR to CR/CRi by 2008 IWCLL criteria
 - c. Cohort 3: determine the response rate (CR/CRi)

Secondary Objectives

1. To determine the safety of nivolumab in combination with ibrutinib in patients with relapsed, refractory or high-risk untreated CLL/Richter transformation (RT).
2. To determine the progression-free survival of patients with relapsed, refractory or high-risk untreated CLL/RT treated with nivolumab in combination with ibrutinib.
3. To determine the overall survival of patients with relapsed, refractory or high-risk untreated CLL/RT treated with nivolumab in combination with ibrutinib.

Exploratory Objectives

1. To study immunological and molecular changes in peripheral blood, lymph node, and bone marrow in response to nivolumab and ibrutinib therapy.

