14.0 STATISTICAL CONSIDERATIONS

EFFICACY

A maximum of 72 patients will be enrolled in this Phase II study. Cohort 1 and 3 will enroll up to 24 patients each who were refractory to or relapsed after at least one prior standard therapy or untreated with del(17p) by FISH; Cohort 2 will enroll up to 24 patients who have been on ibrutinib for at least 9 months and have achieved a partial response.

Note: Statistical analysis and stopping rules, and toxicity assessment for Cohort 3 will be same as Cohort 1.

In the first cohort, the primary objective is to evaluate best response during the first 12-month of therapy. The primary efficacy endpoint, best response (BR), is defined as CR or CRi that occurs during the first 12 months of treatment. The optimum two-stage design proposed by Simon will be implemented.⁵⁶ We assume a target BR rate of 20% and a BR rate of 5% or lower will be considered not desirable. With a type I error rate of 10% and 80% power, we will enroll 9 patients in the first stage. If no patients achieve BR, the trial will be stopped. If 1 or more out of the first 9 patients have BR, accrual will continue until a total of 24 patients have been enrolled. We will suspend accrual at the end of the first stage, if all 9 patients have been enrolled, yet no responder (CR or CRi) has been observed. At the end of the study, if 3 or more out of the 24 patients achieve BR, the combination treatment will be considered efficacious and is worth further investigation. Under this Simon's two-stage design, the probability of early termination is 63% if the true BR is 5% and the expected sample size is 14.6 patients.

In the second cohort, the primary objective is to evaluate conversion rate during the first 12-month of therapy. The primary efficacy endpoint, conversion rate is defined as the conversion from partial response (PR) to complete response (CR/CRi) that occurs during the first 12 months of treatment. Up to 24 patients will be enrolled in this cohort. The same Simon's optimum two-stage design as described above will be used here in cohort 2. We assume a target conversion rate of 20% and a conversion rate of 5% or lower will be considered not desirable. With a type I error rate of 10% and 80% power, we will enroll 9 patients in the first stage. If no patient converts from PR to CR, the trial will be stopped. If 1 or more out of the first

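### Section 10 lets one patient be both PR and CRi (CR with persistent drug-related cytopenia), while the Cohort 1 and 2 primary endpoints count CRi as success and PR as failure, and no text says which label governs

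*Combined protocol and SAP*

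**What the plan says.** Section 10 (Criteria for Response) brings in CRi at two places.

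- Under complete response, after the marrow criterion: "Hypocellular marrow should be noted as" CR with incomplete marrow recovery (CRi). Here CRi is a marrow finding and sits within CR.
- After the partial response criteria: "Additionally, patients who fulfill the criteria above for CR but who have the following will be considered a PR". Two features follow. One is bone marrow nodules, which may be noted as nodular PR. The other is "Patients with persistent anemia or thrombocytopenia or neutropenia apparently unrelated to disease activity and more likely the consequence of persistent drug toxicity", and that bullet ends by allowing the case to be noted as CRi.

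The overall response definition in the same section reads "OR is defined as a CR or PR (or CR with incomplete marrow recovery"), which names CRi apart from PR.

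Section 1 sets the Cohort 1 objective as to "determine the response rate (CR/CRi) by 2008 IWCLL criteria" and the Cohort 2 objective as to "determine the conversion rate from PR to CR/CRi by 2008 IWCLL criteria". In Section 14 the Cohort 1 endpoint, "best response (BR), is defined as CR or CRi that occurs during the first 12 months of treatment", leaves PR out. The Cohort 1 suspension rule repeats the definition: "yet no responder (CR or CRi) has been observed". The Cohort 2 endpoint is likewise conversion to CR/CRi, although its stage-1 stopping sentence mentions CR only.

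**The concern.** A patient who meets every CR criterion except the blood counts, because of persistent drug toxicity, receives two labels from one bullet. The PR label is mandatory in form and the CRi label is permissive. The primary endpoint treats the two labels in opposite ways. In Cohort 1 the patient is a failure as PR and a success as CRi. In Cohort 2 the patient enters as PR, so a PR label means no conversion and a CRi label means conversion.

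Response is assigned by the investigator in an open-label study, and each cohort's decision turns on very small counts. The classification rule should therefore be fixed before anyone sees which patients it affects.

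**Working it through.** **1. The two readings side by side.**

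- *PR governs.* The lead-in to the list is mandatory, and the companion bullet (nodular PR) clearly remains a PR. On this reading, CRi in the endpoint covers only the hypocellular-marrow case.
- *CRi governs.* Sections 1 and 14 define success by the label CRi, Section 14 repeats it in the suspension rule, and the overall response definition keeps CRi separate from PR.

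The second reading fits the endpoint text better. Nothing in Sections 1, 10 or 14 says that it prevails. The references to the 2008 IWCLL criteria and to a modified form of them do not settle it, because the conflict is in the protocol's own written version.

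**2. Reproducing the design.** Inputs from Section 14, the same for both cohorts: n1 = 9, stop at 0 responders; N = 24, success at 3 or more; rates of 5% and 20%. Write p for the counted response rate, X1 ~ Bin(9, p) and X2 ~ Bin(15, p).

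- Stop at stage 1: (1 − p)^9. At 5%, 0.95^9 = 0.630 (stated 63%).
- Expected N: 9 + 15 × (1 − 0.6302) = 14.55 (stated 14.6).
- Success: sum over x from 1 to 9 of P(X1 = x) × P(X2 ≥ 3 − x). At 5% this is 0.0931 (stated type I error 10%). At 20% it is 0.8047 (stated power 80%).

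The design figures reproduce. The problem is what gets counted.

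**3. If cytopenic cases are scored PR.** Let f be the share of true CR/CRi cases that are cytopenic and scored PR. The documents give no value for f; 5% and 10% are assumptions. Counted rate = 0.20 × (1 − f).

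| f | Counted rate | P(0 of 9) | Power |
|---|---|---|---|
| 0 | 20% | 0.80^9 = 13.4% | 80.5% |
| 5% | 19% | 0.81^9 = 15.0% | 77.7% |
| 10% | 18% | 0.82^9 = 16.8% | 74.5% |

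**4. If they are counted but the null excluded them.** Section 14 states 5% for CR or CRi without saying which form of CRi it covers. Suppose 5% meant CR plus hypocellular-marrow CRi only, and cytopenic CRi adds 2.5 percentage points (an assumption). The counted rate under the null is then 7.5%, and the same formula gives a 21.9% chance of success, against 9.3% at 5%.

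**5. Scope.** Cohort 3 is outside this point, because Section 10 sends Richter transformation to the NHL criteria. Overall response is unaffected, since CR, CRi and PR all count towards it.

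**The case against.** The strongest reply is that the endpoint text already answers the question. Success is CR or CRi, a cytopenic patient may be noted as CRi, and so the patient counts. What remains is one loose sentence, and at shares of 5% to 10% the power loss is only about 3 to 6 points. Most of this stands: the intended reading can be inferred and the likely effect is modest. It does not remove the conflict, because an assessor who follows the mandatory wording would score as failures patients whom the endpoint appears to include.

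Four stronger readings might be inferred; the documents do not support them.

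- *That the ambiguity would often change the result.* At a true 20% rate, 30.2% of cohorts have exactly 1 responder in the first 9, and 11.6% continue and finish with exactly 3 of 24 (7.0% are in both groups). These are chances of being one responder from a limit. For the ambiguity to matter, a responder at that limit must also be cytopenic and be labelled PR.
- *That 17% is a usable share.* Section 2.4.3 reports a drug-related decreased platelet count in 17% of 23 Hodgkin's lymphoma patients on nivolumab alone. That is an incidence among treated patients, with persistence not stated. It is not a share of CR/CRi responders in CLL. Much larger shares have no basis in the documents either.
- *That only power is at risk because the 5% null already names CRi.* This assumes CRi has one meaning, which is the point in doubt. Step 4 shows the other direction.
- *That the Cohort 2 stage-1 sentence sets a stricter rule.* It reads as shorthand: the endpoint is defined shortly before it, and the sentences that follow speak of conversion.

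**Conclusion.** The point holds for Cohorts 1 and 2. It is a contradictory classification rule on the primary endpoint that should be corrected; it is not a failure of the two-stage design, whose figures reproduce. One label can change a decision at 1 of 9 or 3 of 24, but how often it would do so cannot be estimated from the documents.

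The illustrations rest on assumed inputs. Scoring 5% or 10% of true CR/CRi cases as PR lowers power by 2.8 or 6.0 points (80.5 − 77.7; 80.5 − 74.5) and raises the chance of a 0-of-9 stop by 1.6 or 3.4 points (15.0 − 13.4; 16.8 − 13.4). Counting such cases against a null that left them out could raise the chance of a false success. The 21.9% figure depends on an assumed 2.5-point addition and does not show that inflation is present.

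**What to change.** Reconcile Sections 10 and 14 with one explicit rule, set before responses are classified.

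1. State whether CR with persistent drug-related cytopenia counts towards the primary endpoint. The reading that fits Sections 1 and 14 is that both forms of CRi (hypocellular marrow, and drug-related cytopenia with all other CR criteria met) are successes for Cohort 1 best response and Cohort 2 conversion. The cytopenia bullet would then leave the PR list and join CRi under CR; nodular PR stays PR.
2. Check the rule against the response criteria that Section 10 cites. They were not available for this review.
3. Confirm that the 5% and 20% rates use the same definition of CRi.
4. Report CR and CRi separately. Section 11.1.3 keeps abnormal blood values off the case report form, so the split should be made from source blood counts.
5. Align the Cohort 2 stage-1 sentence with the CR/CRi wording of its endpoint.

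The cost is mainly wording. No patients, visits or tests are added, and the two-stage limits stand if item 3 confirms the rates. Item 4 needs a check that source records are sufficient.
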